6.8. Identification of Data to Be Recorded on the Case Report Forms

The electronic case report form (eCRF) data will be transcribed from source documentation. No source data will be recorded directly in the eCRF (ie, without prior written or electronic record of data). The transcribed data will be consistent with the source documents or the discrepancies will be explained.

For more information on data handling, refer to Section 15.

⁵ Injection site pain (if resolved 48 hours post vaccination), the size (measured in mm) of erythema, and the occurrence of induration/swelling will not be used as halting criteria.

7. SELECTION AND WITHDRAWAL OF SUBJECTS

7.1. Recruitment of Subjects

Healthy adult men and women will be recruited from the Baltimore-Washington, DC area through the UMB clinical trial centers by use of advertisement in multiple media formats, to include, but not limited to: informational flyers, newspaper advertisements, websites, word of mouth, and e-mail. All recruitment materials will be prepared and submitted for review and approval by the UMB IRB prior to use. When a subject calls the study site and discloses an interest in the study, the recruitment staff will discuss the trial from an IRB-approved script. If the subject is still interested, contact information will be obtained and an appointment for briefing and/or screening will be arranged.

Informed consent will be obtained from each subject prior to any procedures being performed. The study briefing and informed consent process will be done within the respective clinical trial center, which may begin in a group setting, but then proceeds to individual discussion between an investigator and study subject prior to any procedures. Study individuals who are interested in learning about the trial will meet with a member of the study team and will undergo an informed consent process consisting of a detailed informational presentation of the study given by a study investigator or by using IRB-approved briefing slides in person or by means of a pre-recorded audio recording.

Following the briefing, the coordinator or designee will provide the subject ample time to read the informed consent document. A study investigator and/or designee will answer all questions raised during the session. The subject will be asked to sign the consent. The subject will be allowed to take the consent document home to consider and discuss it with others and return to the trial center at a later time to sign it. After signing the consent, the subject will take an assessment of understanding. The assessment is administered to aid the study personnel in identifying gaps in understanding. Subjects must score at least 80% correct on the 10-question multiple-choice questionnaire. Any questions missed will be explained to the subject, and the subject's questions will be answered. The subject will be given one additional opportunity to take the comprehension test. Any subject who, in the opinion of the study investigator, does not understand the study well enough to consider their consent truly informed will be excluded.

No study procedures will occur before the potential subject provides written informed consent. To minimize any possible coercion, supervisors or anyone in the chain of command or in a position of authority will not be permitted to consent the subject. However, they will be available to answer questions and provide additional information.

Consent for Future Use: As part of the informed consent process subjects will be asked to provide permission for the future use of their specimens (see Section 14.3). Refusal to allow samples to be stored for future use will not exclude subjects from participation.

Refer to Section 4.8 for a detailed description of the subject population.

7.2. Eligibility Screening

Each subject must meet all inclusion and no exclusion criteria. Subjects who have signed the informed consent form and successfully completed the assessment of understanding quiz will provide a medical history and undergo a physical examination and clinical safety laboratory tests

administered for screening. The PI or other study physician will make the final decision of the eligibility. Only eligible subjects will be given the investigational product.

Refer to Section 4.8 for a detailed description of the subject population.

7.3. Subject Inclusion Criteria

Subjects must meet all of the following criteria to be included in the study:

1. Healthy adult male or nonpregnant, nonlactating female, ages 18-49 (inclusive) at time of screening.
2. Have demonstrated adequate comprehension of the protocol by achieving a score of at least 80% correct on a short multiple-choice quiz. Individuals who fail to achieve a passing score on the initial quiz will be given the opportunity to retest after a review of protocol information. Individuals who fail the quiz for the second time will not be enrolled.
3. Have provided written informed consent before screening.
4. Free of clinically significant health problems, in the opinion of study investigators, as determined by pertinent medical history and clinical examination before entry into the study. (Refer to Synopsis for full description of terms).
5. Available and able to participate for all study visits and procedures.
6. Sexually active men⁶ and women of childbearing potential⁷ must agree to use an effective method of contraception from 30 days prior to the first study vaccination until 6 months after the last study vaccination.
7. Female subjects agree to not donate eggs (ova, oocytes), and male subjects agree to not donate sperm from the start of screening until at least 6 months after the last vaccination.
8. Female subjects of childbearing potential must have a negative serum pregnancy test at screening and a negative urine pregnancy test within 24 hours prior to each study vaccination.

⁶ A sexually active man is defined as one whose partner is a woman of childbearing potential (see definition below) and has not had a vasectomy performed > 1 year prior to screening. They must agree not to father a child until 6 months after the last vaccination. These subjects must agree to use a barrier method of birth control (eg, either condom with spermicidal foam/gel/film/cream or partner usage of occlusive cap [diaphragm or cervical/vault caps] with spermicidal foam/gel/film/cream/suppository).

⁷ Women of childbearing potential are defined as those who have not been sterilized via tubal ligation, bilateral oophorectomy, bilateral salpingectomy, hysterectomy, or successful Essure® placement (permanent, non-surgical, non-hormonal sterilization) with history of documented radiological confirmation test at least 90 days after the procedure (or with use of another birth control method if history of confirmation test not confirmed), still menstruating or < 1 year of the last menses if menopausal. For this study, an effective contraceptive method is defined as one that results in a failure rate of less than 1% per year when it is used consistently and correctly.

9. Negative hantavirus PsVNA test result at screening.

10. Screening laboratory test values:

- Hemoglobin > 11.0 g/dL for women; > 12.9 g/dL for men
- WBC with differential and platelets either within the normal range (provided by the laboratory performing the analysis) or a Grade 1 deviation from normal (per [Appendix C](#)) and deemed clinically insignificant
- Alanine aminotransferase (ALT), aspartate aminotransferase (AST) and bilirubin < 1.1x upper limit of normal (ULN) (per the normal range provided by the laboratory performing the analysis)
- Serum creatinine < 1.35 g/dL

For all other screening laboratory test values, results that do not meet the definition of a Grade 1-4 value within 56 days prior to enrollment (see [Appendix C](#), “Clinical and Laboratory Toxicity Grading Scales”) are eligible for enrollment.

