- Safety oversight will be conducted by an SMC, which is an independent group of experts that monitors subject safety and advises DMID. SMC members will be separate and independent of study personnel participating in this study and should not have scientific, financial, or other conflicts of interest related to the study. The SMC will consist of at least 3 voting members with appropriate expertise to contribute to the interpretation of safety data from this trial. The SMC will operate under the rules of a DMID-approved charter. The SMC will review applicable data to include but not limited to enrollment, demographics, dosing, and clinical and safety data, which may include solicited and unsolicited AEs/SAEs, reactogenicity, concomitant medications, clinical safety laboratory values, and any physical examinations at scheduled time points during the study as defined in the charter. The objective of the SMC is to make recommendations to the sponsor if the study should continue per protocol, be modified and then proceed, or be

terminated. After each meeting the SMC will make its recommendations in writing to the sponsor regarding continuation, modification, or termination of the clinical trial.

SMC meetings for data review are as follows:

1. Organizational meeting (prior to start of the study)
2. An SMC ad hoc meeting will be convened when a halting rule is met or at the request of the investigator and/or DMID if there are safety concerns during the course of the study
3. Annual review meetings.
4. End of study safety data review (after database lock and prior to final clinical study report)
5. Data will be provided in a standard summary format. The SMC may be asked to provide recommendations in response to questions posed by DMID.

^a Good health is defined by the absence of any medical condition described in the exclusion criteria in a subject with a normal abbreviated physical examination including vital signs. If the subject has another current, ongoing medical condition, the condition cannot meet any of the following criteria: (1) first diagnosed within 3 months of enrollment, (2) is worsening in terms of clinical outcome in last 6 months, or (3) involves need for medication that may pose a risk to subject's safety or impede assessment of adverse events or immunogenicity if they participate in the study.

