^c Safety lab results will not be reviewed prior to product administration, and inclusion/exclusion criteria will be applied, with the exception of exclusion criteria 9, which will not be applied for vaccinations 2 and 3 because it is for screening prior to enrollment.

^d Physical examination will be completed at screening visit 1, and includes examination of general appearance, skin, neck (including thyroid), eyes, nose, throat, lungs, heart, abdomen, lymph nodes, extremities, and a basic neurological assessment; directed physical exams will be completed at all other visits. A directed physical exam is defined as a focus, complaint-driven physical examination. In the absence of a complaint, a physical exam will not be performed.

^e Reactogenicity assessments will include subject completion of a memory aid each day for 14 days after a vaccination visit.

^f Vital sign measurements include oral temperature, heart rate, respiratory rate, and systolic and diastolic blood pressure.

^g Complete blood count (CBC [WBC, Hb, platelets] with differential), glucose, creatinine, AST, ALT, total bilirubin. Lab abnormalities will be followed up on an ad hoc basis as per the study investigators. At Screen 1, a collection of 2.7 mL blood will be used to perform the PT/PTT tests to determine any coagulation abnormalities for exclusion criterion 25.

^h Blood will be drawn prior to study product administration. Safety lab results will not be reviewed prior to product administration.

ⁱ Approximately 10 mL of blood will be collected at Screen 2 to determine subject eligibility.

^j Blood collected for the humoral immune response to vaccination will be approximately 10 mL on Days 0, 28, 56 and 140; any remaining blood will be stored for future use. Approximately 50 mL of blood will be collected on Day 84 for humoral immune response to vaccination and for future use.

For determination of any cardiac abnormalities, an ECG will be performed at Screen 1 and study visit 11.

ⁿ Procedures will be completed only if Screen Visit 2 falls outside of the 56-day screening window prior to vaccination. See Section 8.1.2 for further clarification

^o Scripted telephone contact for collection of Serious Adverse Event information

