13. Any confirmed or suspected immunosuppressive or immunodeficient condition, including HIV infection or use of anticancer chemotherapy or radiation therapy (cytotoxic) in the 3 years prior to screening.
14. Administration of chronic (defined as more than 14 days) immunosuppressants or other immune-modifying drugs within 6 months of screening. For corticosteroids, this will mean prednisone, or equivalent, greater than or equal to 5 mg/day. Intranasal, inhaled (< 800 beclomethasone mcg/day), and topical steroids are allowed.
15. Has current or past diagnosis of schizophrenia, bipolar disease, or other psychiatric diagnosis that may interfere with subject compliance or safety evaluations.
16. Has been hospitalized for psychiatric illness, history of suicide attempt, or confinement for danger to self or others within 10 years prior to screening.
17. Any chronic or active neurologic disorder, including Guillain-Barré syndrome, seizures and epilepsy, excluding a single febrile seizure as a child.
18. Syncopal episode within 12 months of screening.
19. Suspected or known current alcohol and/or illicit drug abuse within the past 5 years based on self-reporting and physical exam.
20. Any medical, psychiatric, social condition, occupational reason, or other responsibility that, in the judgment of the investigator, is a contraindication to protocol participation or impairs a subject's ability to give informed consent or to comply with the protocol schedule.
21. Pregnant or lactating female, or subject plans to father a child or become pregnant during the study period.

22. Current employee or staff paid entirely or partially by the contract for this trial, or staff who are supervised by the PI or subinvestigators.
23. Subjects with implanted electronic devices stimulation device, such as cardiac demand pacemakers, automatic implantable cardiac defibrillator, nerve stimulators, or deep brain stimulators.
24. Bleeding diathesis or condition associated with prolonged bleeding time, as determined through measurement of PT/PTT (prothrombin time/partial thromboplastin times) during screening labs, that would contraindicate ID or an IM injection.
25. History of cardiac arrhythmia or palpitations or abnormal arrhythmia noted on ECG performed at screening (eg, supraventricular tachycardia, atrial fibrillation, frequent ectopy) prior to study entry. Measurement of sinus bradycardia (ie, < 50 beats per minute on exam) at screening.
26. History of diabetes type 1 or 2

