APPENDIX B. SENTINEL SUBJECT ENROLLMENT PROCESS

Randomization Figure pertaining to Amendments 1.0-4.0 (maintained in this document for reference).

Randomization Figure pertaining to Protocol Version 6.0 and future versions. These activities will proceed since completion of enrollment and vaccinations for Groups 2 and 4 and sentinels for Group 6 (n=36 already enrolled by March of 2020). The Randomization Scheme describes plan for enrollment in Nov 2021 of sentinel participants in Group 5 (n=2), then enrollment of Groups 1 and 3 (n=24) and Groups 5 and 6 (n=20).

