^b Defined as a disorder characterized by lymph node enlargement after vaccination.

C-2 TABLE FOR LABORATORY ABNORMALITIES

Table C-5: FDA Toxicity Grading Scale – Serum and Hematology Laboratory Abnormalities

Laboratory Test ^a	Mild (Grade 1)	Moderate (Grade 2)	Severe (Grade 3)	Potentially Life Threatening (Grade 4) ^b
Glucose – Hypoglycemia (mg/dL)	65-69	55-64	45-54	< 45
Glucose – Hyperglycemia Fasting (mg/dL) Random (mg/dL)	106-110 121-125	111-125 126-200	> 125 > 200	Insulin requirements or hyperosmolar coma
Creatinine (mg/dL) (Female)	1.15-1.7 ^c	1.8-2.0	2.1-2.5	> 2.5 or requires dialysis
Creatinine (mg/dL) (Male)	1.35-1.7	1.8-2.0	2.1-2.5	> 2.5 or requires dialysis
Liver Function Tests – ALT, AST Increase by factor	1.1-2.5 x ULN ^d	2.6-5.0 x ULN	5.1-10 x ULN	> 10 x ULN
Bilirubin – When accompanied by any increase in liver function test Increase by factor	1.1-1.25 x ULN	1.26-1.5 x ULN	1.51-1.75 x ULN	> 1.75 x ULN
Bilirubin – when liver function test is normal; increase by factor	1.1-1.5 x ULN	1.6-2.0 x ULN	2.0-3.0 x ULN	> 3.0 x ULN
Hemoglobin (Female) (gm/dL)	11.0-11.9 ^c	9.5-10.9	8.0-9.4	< 8.0
Hemoglobin (Female)	Any decrease-1.5	1.6-2.0	2.1-5.0	> 5.0

Laboratory Test ^a	Mild (Grade 1)	Moderate (Grade 2)	Severe (Grade 3)	Potentially Life Threatening (Grade 4) ^b
change from baseline value (gm/dL)				
Hemoglobin (Male) (gm/dL)	12.5-13.4 ^c	10.5-12.4	8.5-10.4	< 8.5
Hemoglobin (Male) change from baseline value (gm/dL)	Any decrease-1.5	1.6-2.0	2.1-5.0	> 5.0
WBC Increase (cell/mm ³)	10,100-15,000 ^c	15,001-20,000	20,001-25, 000	> 25,000
WBC Decrease (cell/mm ³)	2,500-3,950 ^c	1,500-2,499	1,000-1,499	< 1,000
Lymphocytes Decrease (cell/mm ³)	750-1000	500-749	250-499	< 250
Neutrophils Decrease (cell/mm ³)	1,500-1,559	1,000-1,499	500-999	< 500
Eosinophils (cell/mm ³)	501-1,500	1,501-5000	> 5,000	Hypereosinophilic
Platelets Decreased (cell/mm ³)	125,000-139,500	100,000-124,000	25,000-99,000	< 25,000

^a The laboratory values provided in the tables serve as guidelines and are dependent upon institutional normal parameters. Institutional normal reference ranges should be provided to demonstrate that they are appropriate.

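### The serum creatinine inclusion limit is printed in g/dL instead of mg/dL in both places it appears, so read literally it excludes nobody on creatinine

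*Protocol*

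**What the plan says.** Item 10 of the inclusion criteria lists screening laboratory limits. For creatinine, Section 7.3 reads "Serum creatinine < 1.35 g/dL", and Synopsis inclusion 10d prints the same limit and unit. Item 10 closes with a general rule that begins "For all other screening laboratory test values, results that do not meet the definition of a Grade 1-4 value" and makes such results acceptable for enrollment.

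Table C-5 in Appendix C grades creatinine separately for women and men, both in mg/dL. The men's row begins "Creatinine (mg/dL) (Male" and puts Grade 1 at 1.35-1.7. The women's row puts Grade 1 at 1.15-1.7. Grade 4 is above 2.5, or a need for dialysis, in both rows.

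Section 7.2 makes the criteria binding: "Each subject must meet all inclusion and no exclusion criteria". The notes to Table 4 (footnotes c and h) add that, at vaccination visits, "Safety lab results will not be reviewed prior to product administration".

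**The concern.** The number 1.35 matches Table C-5 exactly, but the unit does not. A limit in g/dL lies far beyond any value the protocol's own scale contemplates, so the criterion as printed cannot screen anyone out.

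This matters because the line is an entry threshold, not background text. Source checks, monitoring and deviation calls are made against the printed criteria. A subject with a screening creatinine of 2.0 mg/dL, which is Grade 2, would satisfy item 10 as written, and a site applying the intended limit would be departing from the approved wording. Because Day 0 safety laboratory results are not looked at before dosing, the screening value is the laboratory check that stands before the first dose.

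**Working it through.** **Inputs**

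- Printed limit: 1.35 g/dL (Synopsis 10d; Section 7.3, item 10).
- Table C-5, in mg/dL: male Grade 1 starts at 1.35, female Grade 1 starts at 1.15, Grade 4 is above 2.5.
- Conversion: 1 g/dL = 1000 mg/dL.

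**Size of the misprint**

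- Printed limit: 1.35 × 1000 = 1350 mg/dL.
- Against male Grade 1: 1350 / 1.35 = 1000.
- Against female Grade 1: 1350 / 1.15 ≈ 1174.
- Against Grade 4: 1350 / 2.5 = 540.

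**Eligibility under each reading**

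| Screening creatinine (mg/dL) | As printed (< 1350 mg/dL) | If mg/dL is meant (< 1.35 mg/dL) |
|---|---|---|
| 1.0 | passes | passes |
| 1.34 | passes | passes |
| 1.35 | passes | fails |
| 2.0 | passes | fails |
| 2.5 | passes | fails |
| 10 | passes | fails |
| 50 | passes | fails |

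The figure of 1.35 agrees with Table C-5 only in mg/dL, where it is the lower edge of male Grade 1.

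**Does any other rule supply a limit?**

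- The general rule in item 10 covers "For all other screening laboratory test values, results that do not meet the definition of a Grade 1-4 value". Creatinine has its own line in item 10, so it is not among the other tests.
- Section 8.1.2 allows one reassessment of out-of-range screening values but makes an exception for those named in item 10.
- SAP Section 4.6 requires creatinine at or below the upper limit of normal, with no number or unit. The SAP is dated January 2019 and plans up to 72 subjects rather than 82. It shows that a real limit was intended, but the protocol governs eligibility.

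What remains is judgment. Inclusion 4, read with Synopsis footnote a, bars an ongoing condition that was "first diagnosed within 3 months of enrollment". Exclusion 20 removes anyone with a medical condition that, "in the judgment of the investigator, is a contraindication to protocol participation". A study physician makes the final eligibility decision (Section 7.2).

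**Subjects still to be screened under this text**

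Appendix B reports 36 already enrolled by March 2020. It then plans 2 Group 5 sentinels, 24 subjects in Groups 1 and 3, and 20 in Groups 5 and 6. Section 6.2 makes the last 20 conditional on completing their enrollment within 4 months.

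- Lower bound: 2 + 24 = 26 (total 36 + 26 = 62).
- Upper bound: 26 + 20 = 46 (total 36 + 46 = 82, the stated maximum).

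**The case against.** The strongest reply is that this is a self-evident misprint with no real consequence. No study physician would take the limit to be 1350 mg/dL. Item 10 itself sends the reader to Appendix C, where the correct unit stands beside the same number. Inclusion 4, exclusion 20 and the physician's decision would stop anyone with clinically significant renal impairment. Laboratory adverse events are graded from Table C-5, whose unit is correct, and nothing statistical changes. Leaving Day 0 results unread before dosing applies to all the safety tests, and Section 8.1.1 already requires a recheck when screening results are more than 56 days old.

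All of that stands, and it is why the practical risk is low. It does not make the printed criterion right. The remaining safeguards are discretionary, whereas item 10 was written to give a numeric limit.

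A further objection is that the correction leaves a separate gap: in mg/dL, a single limit of 1.35 still admits women from 1.15 to below 1.35, who are Grade 1 in Table C-5. That is true, but it is a different question and no reason to leave the unit wrong.

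**Conclusion.** The point holds. The creatinine inclusion limit is misprinted in both protocol locations by a factor of 1000, and followed literally it excludes nobody on creatinine. This rests on the unit conversion and on Table C-5 showing which unit was meant; it needs no outside figure.

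The factor of 1000 measures the misprint, not harm. The documents give no basis for estimating how many subjects, if any, would be wrongly enrolled. The range of 26 to 46 counts those still to be enrolled and is not an estimate of errors. Nothing is claimed about the 36 already enrolled, because the documents do not show which protocol version introduced the g/dL text. The laboratory adverse event endpoint, the sample size and the analysis sets are unaffected. The correction should be made, but the error does not threaten the trial's conclusions.

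**What to change.** Replace g/dL with mg/dL for creatinine in Synopsis inclusion 10d and in Section 7.3, item 10, so that both read < 1.35 mg/dL. The hemoglobin limits in the same item are correctly in g/dL and should stay. The cost is a unit correction in two places, with no change to design, visits or analysis.
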